2.4 Rationale

Talimogene laherparepvec and pembrolizumab blockade likely play complementary roles in regulating adaptive immunity. Talimogene laherparepvec likely augments dendritic cell-mediated tumor antigen presentation through local expression of GM-CSF ([Kaufman et al, 2010](#)) and local antigen release by direct tumor lysis. PD-1 plays an important role in SCCHN. Pembrolizumab is a PD-1 regulator and prevents T-cell exhaustion in peripheral tissues. After evidence of activity in SCCHN, pembrolizumab is being evaluated in 2 phase 3 trials.

The combination of an agent that increases tumor-specific immune activation (talimogene laherparepvec) with one that blocks inhibitory T-cell checkpoints (pembrolizumab) could produce greater antitumor activity than either agent alone.

There are currently 2 ongoing combination immunotherapy studies with talimogene laherparepvec and a checkpoint inhibitor in advanced stage melanoma. The first is a phase 1b/2 study of ipilimumab with or without talimogene laherparepvec in unresected melanoma (NCT01740297). In the phase 1b portion, 18 of 19 subjects (more than half with stage IV M1b disease) received both talimogene laherparepvec and ipilimumab in combination. Full dose of talimogene laherparepvec and ipilimumab 3 mg/kg every 3 weeks starting at week 6 were tolerable. Per immune-related response criteria (data cutoff of 22 December 2014), the ORR in 18 evaluable subjects was 56% (33% complete responses [CRs]), and the durable response rate (DRR) was 44%. Median PFS was 10.6 months (2.6 to 19.3+ months). Median OS was not reached; 12-month and 18-month survival rates were 72.2% and 67%, respectively. On a lesion level, 8 and 5 of 16 uninjected index lesions regressed \geq 50% and 100%, respectively. Grade 3/4 treatment-emergent A occurred in 32% of subjects, and grade 3/4 immune-related adverse events occurred in 2 subjects (grade 3 hypophysitis and adrenal insufficiency; and grade 4 amylase + lipase elevations). There were no treatment-related deaths ([Puzanov et al, 2014](#)). More recently, an interim analysis of the phase 2 portion of the study which was performed when 82 patients had \geq 48 weeks of

follow up was reported ([Chesney et al, 2016](#)). One-hundred and seventy three subjects were randomized: 88 in the talimogene laherparepvec + ipilimumab arm and 85 in the ipilimumab arm. Characteristics for all subjects were similar: 54% stage IIIB-IVM1a, 45% IVM1b/c. Median follow up time for 82 subjects was 61.2 weeks (range: 0.14-113.9). Confirmed ORR was 35.7% in the combination arm and 17.5% in the ipilimumab arm with odds ratio for response of 2.6 (95% CI; 0.9-7.3). Unconfirmed ORR was 50% in the combination arm and 27.5% in the ipilimumab arm. Safety data in the analysis were as expected based on the phase 1b data; of 165 subjects in the safety set (85 in the combination arm and 80 in the ipilimumab arm), the incidences of grade 3 and 4 treatment related adverse events were similar in both arms (total of 20% in the combination arm and 19% in the ipilimumab arm) with the exception of diarrhea (4% in combination arm vs 0% in ipilimumab arm) and colitis (4% in combination arm vs 8% in ipilimumab arm). A grade 5 autoimmune hepatitis occurred in the combination arm which was attributed to ipilimumab per investigator.

The second study is a phase 1b/3 multicenter open-label trial of talimogene laherparepvec in combination with pembrolizumab for treatment of unresected, stage IIb to IVM1c melanoma (NCT02263508). In the phase 1b portion of the study, subjects with stage IIb-IV melanoma with injectable lesions and no prior systemic therapy received up to 4.0 mL of talimogene laherparepvec monotherapy for 2 doses followed by talimogene laherparepvec and pembrolizumab every 2 weeks thereafter. All 21 evaluable subjects had an adverse event: 29% grade 3, no grade 4 and 1 grade 5 (not treatment related). The most common adverse events by preferred term were fatigue (52%), pyrexia (48%), chills (43%), and rash (38%). Of 16 subjects evaluable for response, the unconfirmed response rate per investigator was 56%; DCR was 69% (12.5% CR, 44% partial response [PR], 12.5% stable disease [SD]) ([Long et al, 2015](#)).

This registrational study is intended to provide evidence that a regimen of an oncolytic immunotherapy (talimogene laherparepvec) and a checkpoint inhibitor (pembrolizumab) is safe and tolerable, and that the combination might enhance the clinical efficacy of single agent pembrolizumab in recurrent or metastatic SCCHN. The choice of PD-1 inhibitors for the control arm is based on the assumption that this class of agent may become the new standard of care in this indication. The study is an accelerated design leading from a phase 1b to a phase 3 study without a conventional phase 2 evaluation. However, activity of the combination will be evaluated at the end of the phase 1b study to support a decision to initiate the phase 3 study.

2.5 Clinical Hypotheses

Phase 1b:

Talimogene laherparepvec in combination with pembrolizumab will be safe and well tolerated in subjects with recurrent or metastatic SCCHN.

Phase 3:

The clinical hypothesis is that talimogene laherparepvec with pembrolizumab compared to placebo with pembrolizumab will improve OS. In addition to the hypothesis test for the primary endpoint, ORR, PFS, iORR, and iPFS in subjects given talimogene laherparepvec plus pembrolizumab versus placebo plus pembrolizumab will be compared.

3. EXPERIMENTAL PLAN

3.1 Study Design

This is a phase 1b/3, multicenter clinical trial. The study will be conducted in 2 parts (phase 1b and phase 3) as described below. The overall study design is described by a [Study Design and Treatment Schema](#) at the end of the protocol synopsis section.

The study endpoints are defined in [Section 10.1.1](#).

3.1.1 Phase 1b Study Design

Phase 1b is a multicenter, single-arm study. Talimogene laherparepvec will be administered in combination with pembrolizumab to approximately 40 subjects with recurrent or metastatic SCCHN. DLT will be evaluated based on first 18 DLT-evaluable subjects. An expansion cohort of up to an additional 22 treated subjects will be enrolled to obtain a total of approximately 40 treated subjects to further evaluate the safety and to estimate the efficacy of the combination of talimogene laherparepvec with pembrolizumab to support a decision to initiate the phase 3 study.

3.1.1.1 Rules for DLT Evaluation in Phase 1b

A Dose Level Review Team (DLRT) will review the safety data to evaluate DLT. This team will recommend either to enroll more subjects for DLT evaluation in phase 1b, to prematurely stop enrollment into phase 1b, or to declare that the combination is tolerable based on the criteria described in [Table 1](#) below.

The DLT evaluation period is 6 weeks from the initial administration of study treatment. To be evaluable for a DLT, subjects must have had the opportunity to be on treatment for at least 6 weeks from the initial dosing of study treatment and have received at least 2 doses of talimogene laherparepvec and 2 doses of pembrolizumab in combination, or

have a DLT during the DLT evaluation period after at least 1 dose of talimogene laherparepvec and pembrolizumab in combination. Subjects may be replaced if they are not evaluable for DLT to obtain 18 DLT-evaluable subjects (eg, a subject did not receive study treatment, or ended the study treatment before completion of DLT evaluation period for a reason other than experiencing a DLT).

Safety will be evaluated considering the incidence of DLTs among all DLT-evaluable subjects enrolled in the phase 1b. A sequential stopping rule is derived based on a hypothesis testing approach considering only the first 18 DLT-evaluable subjects (Goldman, 1987). There will be up to 3 planned safety interim analyses. The cumulative increments of DLT-evaluable subjects and corresponding acceptable maximum number and percentage of DLTs at each analysis are indicated in Table 1. The combination will not be declared safe if the number of DLTs exceeds the acceptable maximum number and phase 1b will stop.

Table 1. Cumulative Increments of DLT-evaluable Subjects and Corresponding Acceptable Maximum Number and Percentage of DLTs at Each Planned Interim Safety Analysis

Analysis	Number DLT Evaluable Subjects	Number DLT Evaluable	Acceptable Maximum Number (%) of DLTs
#1	First 4 to 6	4	2 (50)
		5	2 (40)
		6	2 (33)
		7 ¹	2 (29)
#2	4 to 6 new after Analysis #1	8	2 (25)
		9	3 (33)
		10	3 (30)
		11	3 (27)
		12	3 (25)
		13 ¹	3 (23)
#3	Exactly 18 total	18 ²	4 (22)

DLT = dose limiting toxicity

The design achieves a 7.7% 1-sided significance level and 81.6% power to test the null hypothesis of a DLT rate $\leq 10\%$ versus the alternative hypothesis of a rate $\geq 33\%$.

¹ Although the target is 4 to 6 DLT-evaluable subjects at Analysis #1, and 4 to 6 new subjects at Analysis #2, all DLT-evaluable subjects will be included in each analysis.

² If > 18 subjects receive the combination they will contribute to the overall safety analysis, but only the first 18 DLT-evaluable will be considered in the decision to declare the combination safe.

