The first dose of talimogene laherparepvec will be up to 8.0 mL of 10^6 PFU/mL. The second injection, up to 8.0 mL of 10^8 PFU/mL, will be administered 3 weeks (+3 days) after the initial injection (ie, no sooner than day 22 but should not be delayed more than 3 days after the 3 week time point). All subsequent injections, up to 8.0 mL of 10^8 PFU/mL, will be administered every 3 weeks (\pm 3 days). The maximum volume of talimogene laherparepvec administered at any dose is 4.0 mL for any individual tumor lesion. The maximum volume in any treatment visit is 8.0 mL. When talimogene laherparepvec and pembrolizumab are administered on the same day, it is recommended that talimogene laherparepvec be administered first. Refer to [Section 6.2.1](#).

Phase 3:

The initial dose of double-blind treatment is up to 8.0 mL of 10^6 PFU/mL talimogene laherparepvec/placebo (talimogene laherparepvec formulation excipients as described in the Talimogene Laherparepvec [Investigator's Brochure](#)). The second dose up to 8.0 mL of 10^8 PFU/mL talimogene laherparepvec/placebo should be administered 21 (+ 3) days after the initial dose. Subsequent doses up to 8.0 mL of 10^8 PFU/mL talimogene laherparepvec/placebo should be given every 3 weeks (\pm 3 days). The maximum volume of talimogene laherparepvec/placebo administered at any dose is 4.0 mL for any individual tumor lesion. The maximum volume at any treatment visit is 8.0 mL. When talimogene laherparepvec/placebo and pembrolizumab are administered on the same day, it is recommended that talimogene laherparepvec/placebo be administered first.

Non-Amgen Investigational Product Dosage and Administration: Pembrolizumab will be manufactured by Merck. Pembrolizumab is supplied in 100 mg/4mL vials (25 mg/mL) solution for intravenous infusion.

Phase 1b/3:

Pembrolizumab at a dose of 200 mg will be administered intravenously every 3 weeks (\pm 3 days). See [Section 6.2.2.2](#) for additional information regarding dosage and administration of pembrolizumab.

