3.1.1.2 Definition of DLT in Phase 1b

All toxicities will be graded using the CTCAE version 4.0 (Appendix A).

The occurrence of any of the following toxicities during DLT evaluation period (ie, 6-week period from the initial administration of talimogene laherparepvec and

pembrolizumab in combination) will be considered a DLT, if judged by the investigator to be related to the administration of talimogene laherparepvec and/or pembrolizumab:

- Grade 4 non-hematologic (non-laboratory) toxicity
- Grade 3 or higher pneumonitis
- Grade 3 non-hematologic (non-laboratory) toxicity lasting > 3 days despite optimal supportive care
- Grade 3 fatigue will not be classified as DLT, irrespective of duration
- Any grade 3 or higher non-hematologic laboratory value if:
 - medical intervention is required, or
 - the abnormality leads to hospitalization, or
 - the abnormality persists at grade 3 or higher for >1 week unless deemed not clinically important per both investigator and sponsor
- Grade 3 or grade 4 febrile neutropenia
- Thrombocytopenia < 25 x 10⁹/L associated with bleeding event requiring intervention
- Serious herpetic event:
 - Herpetic encephalitis, encephalomyelitis, or disseminated herpetic infection
- Grade 5 toxicity (ie, death)
- Any other intolerable toxicity leading to permanent discontinuation of talimogene laherparepvec or pembrolizumab

If a subject experiences a DLT during the DLT evaluation period, study treatments will be discontinued for that subject.

An expansion cohort of up to 22 treated subjects will be enrolled so there will be approximately 40 treated subjects in total to estimate the efficacy of the combination of talimogene laherparepvec with pembrolizumab.

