6.2.1.1 Dosage, Administration, and Schedule

Talimogene laherparepvec/placebo must be prepared and administered by a qualified healthcare professional. Subjects should be assessed clinically for adverse events/toxicity prior to each dose using the CTCAE version 4 ([Appendix A](#)). Complete blood count with differential and chemistry panels including liver function laboratory tests (ALT, AST, and total bilirubin) should be obtained according to the Schedule of Assessments ([Table 5](#) and [Table 7](#)) and the results should be checked before each treatment. For subjects on anticoagulant therapy, close monitoring of coagulation parameters is recommended during the study treatment phase. Dosing will occur only if these test values are acceptable per [Section 6.2.1.2](#).

Talimogene laherparepvec/placebo will be administered by intralesional injection only into injectable cutaneous, subcutaneous, and nodal tumors, with or without image ultrasound (US) guidance. Talimogene laherparepvec/placebo must not be administered into the mucosal surface of tumor lesions or visceral metastases. For subjects with tumor(s) which directly contacts or encases a major vessel but does not have ulceration and/or fungation onto the skin surface, talimogene laherparepvec injections should be given no closer than 2 cm from the wall of the major vessel. This should be done under image guidance and by skilled personnel (eg, a surgeon).

For the first cycle, the dose of talimogene laherparepvec/placebo will be up to 8.0 mL of 10^6 PFU/mL administered on week 0, day 1. For the second cycle, subjects may receive up to 8.0 mL of talimogene laherparepvec 10^8 PFU/mL or placebo 3 weeks (+ 3 days) after the initial injection (ie, no sooner than day 22 but should not be delayed more than 3 days after the 3 week time point). All subsequent doses up to 8.0 mL of talimogene

laherparepvec 10^8 PFU/mL or placebo will be administered every 3 weeks (\pm 3) days. If a delay of > 3 days is anticipated due to reasons other than toxicity, permission should be sought from the medical monitor. The treatment cycle interval may be increased due to toxicity as described in [Section 6.2.1.2](#). It is recommended that talimogene laherparepvec/placebo be administered before pembrolizumab on treatment days.

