6.2.1.2 Dosage Adjustments, Delays, Rules for Withholding or Restarting, Permanent Discontinuation

Dose reductions of talimogene laherparepvec/placebo are not permitted, other than with respect to a reduction in the volume injected due to a disease response.

If a subject experiences any of the following treatment-related toxicities, administration should be delayed until the toxicity has resolved to at least CTCAE grade 1 or baseline:

- grade 2 or greater immune-mediated adverse events, with the exception of vitiligo
- grade 2 or greater allergic reactions
- any other grade 3 or greater hematologic or non-hematologic toxicity

Talimogene laherparepvec should be withheld if subject experiences any adverse event which, in the opinion of the investigator, warrants withholding investigational product.

If the subject requires corticosteroid dosing of > 10 mg prednisone daily (or equivalent) for related toxicities, talimogene laherparepvec/placebo dosing must be withheld until the corticosteroid dose has decreased to ≤ 10 mg prednisone daily (or equivalent).

All necessary supportive therapies except for those listed in [Section 6.9](#) shall be available to subjects. Talimogene laherparepvec/placebo treatment should be continued based on the potential benefit/risk assessment of the subject.

If talimogene laherparepvec/placebo dosing is delayed by more than 4 weeks from the date of the planned dose (ie, approximately 7 weeks since the previous dose) due to the occurrence of an adverse event that is considered related to talimogene laherparepvec/placebo, the subject must be permanently withdrawn from talimogene laherparepvec/placebo treatment. If talimogene laherparepvec/placebo dosing is delayed by more than 4 weeks from the date of the planned dose (ie, 7 weeks from the previous dose) for reasons other than treatment-related toxicity, the case must be reviewed by the sponsor medical monitor in conjunction with the investigator to determine if the subject can resume talimogene laherparepvec/placebo treatment.

Talimogene laherparepvec/placebo doses may be given no less than 15 days apart, if needed, for the purpose of re-aligning dosing schedules after a dose delay.

Talimogene laherparepvec in phase 1b or talimogene laherparepvec/placebo in phase 3 is to be permanently discontinued for subjects meeting any of the following criteria:

- Phase 1b subject developed DLT during the DLT evaluation period.

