7.1 DLT Analysis Set

The DLT analysis set will include DLT-evaluable subjects who have had the opportunity to be on treatment for at least 6 weeks from the initial dosing of study treatment and have received at least 2 doses of talimogene laherparepvec and 2 doses of

pembrolizumab in combination, or have a DLT during the DLT evaluation period after at least 1 dose of talimogene laherparepvec and pembrolizumab in combination.

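### A subject whose second dose is delayed by toxicity can be counted as DLT-free with little or no observation after the first 10^8 PFU/mL dose

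*Protocol*

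**What the plan says.** **Window.** Protocol 3.1.1.1: "The DLT evaluation period is 6 weeks from the initial administration of study treatment". Section 3.1.1.2 keeps the same starting point: "6-week period from the initial administration of talimogene laherparepvec and" pembrolizumab.

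**Dose sequence.** The phase 1b dosing text states: "The first dose of talimogene laherparepvec will be up to 8.0 mL of 10^6 PFU/mL". Dose 2 is the first at 10^8 PFU/mL. Section 6.2.1.1 schedules it "no sooner than day 22 but should not be delayed more than 3 days after the 3 week time point", and then adds: "The treatment cycle interval may be increased due to toxicity".

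**Delay.** Section 6.2.1.2 lists related toxicities (grade 2 or greater immune-mediated or allergic events, other grade 3 or greater toxicity) for which "administration should be delayed until the toxicity has resolved to at least CTCAE grade 1 or baseline". Withdrawal is mandatory only when a related delay passes 4 weeks from the planned date, about 7 weeks after the previous dose.

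**Evaluability.** A subject without a DLT must have had the opportunity for 6 weeks on treatment and, in the words of SAP 7.1, "have received at least 2 doses of talimogene laherparepvec and 2 doses of" pembrolizumab. Protocol 3.1.1.1 and 10.1.2.1 set the same condition. None of the three gives a date by which dose 2 must be received or a time for which the subject must be observed after it.

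**Replacement.** Non-evaluable subjects may be replaced. The examples are subjects who were never treated or who ended treatment early for a reason other than a DLT.

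**The concern.** DLT incidence is the phase 1b primary endpoint, and Table 1 uses the DLT count to decide whether the combination is tolerable. The window is meant to cover both concentrations, and on schedule it does. When dose 2 is late, the window still closes at 6 weeks, so the lost time is all time at the higher concentration. A toxicity on day 55 in a subject who received dose 2 on day 50 would fall outside the window, and the subject would still be in the denominator as DLT-free.

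The loss does not fall evenly. The subjects affected are mainly those who have already had related toxicity. The replacement rule does not catch them, because they have not ended treatment and they meet the evaluability conditions.

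**Working it through.** **1. Time left after dose 2.** Dose 1 is day 1, so the 6-week mark is 1 + 42 = day 43. Days left = max(0, 43 − day of dose 2).

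| Dose 2 on day | Delay from day 22 | Days left |
|---|---|---|
| 22 | 0 | 21 |
| 25 | 3 | 18 |
| 36 | 14 | 7 |
| 42 | 20 | 1 |
| 43 | 21 | 0 |
| 50 | 28 | 0 |

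The limit for a related event is 22 + 28 = day 50.

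**2. Can the delay occur without a DLT?** Yes. Grade 2 immune-mediated events and uncomplicated grade 3 cytopenia require a delay under 6.2.1.2 but are not on the DLT list in 3.1.1.2. Related grade 3 fatigue also requires a delay, and 3.1.1.2 says it is not a DLT. Section 6.2.1.2 also withholds talimogene laherparepvec while prednisone for related toxicity exceeds 10 mg daily, and Table 3 asks for a taper over at least 4 weeks. A delay of several weeks is therefore foreseeable.

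**3. The plan's own figures.** Protocol 3.1.1.1 states a 7.7% one-sided level at a DLT rate of 10% and 81.6% power at 33%. Exact binomial enumeration gives 7.66% and 81.58% if the count is checked after every subject, with maxima of 2 (n = 4 to 8), 3 (n = 9 to 13) and 4 (n = 14 to 18), plus a maximum of 1 at n = 2 to 3. The maxima at n = 2 to 3 and n = 14 to 17 are not in Table 1; they are inferred. With three looks at 6, 12 and 18 and the printed limits (stop if DLTs exceed 2, 3, 4), the result is 4.6% and 78.8%. The three-look version is the base below because Table 1 describes three analyses.

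**4. Effect on the chance of stopping.** Assumptions: true DLT rate 33%; a share s of that risk arises only after the first 10^8 PFU/mL dose; k of 18 subjects are counted with no observation after dose 2. The documents give neither s nor k. An affected subject has an observable DLT probability of 0.33 × (1 − s); the others have 0.33. The stopping probability is computed exactly and averaged over all placements of the k subjects.

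| | s = 25% | s = 50% | s = 100% |
|---|---|---|---|
| k = 0 | 79% | 79% | 79% |
| k = 2 | 76.5% | 74% | 69% |
| k = 3 | 75% | 71% | 63% |

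The expected DLT count among 18 falls from 18 × 0.33 = 5.94 by k × s × 0.33. With k = 2 and s = 100%, it is 5.94 − 0.66 = 5.28.

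Under the every-subject rule that reproduces 81.6%, the pattern is the same. With s = 50%, power is 77.3% (k = 2) or 74.9% (k = 3); with s = 100%, it is 72.6% or 67.2%.

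**The case against.** **The protocol does schedule dose 2.** Section 6.2.1.1 allows only 3 days beyond the 3-week point, so it would be wrong to infer that dose 2 has no set time. But that is a dosing rule that gives way to toxicity; it is not a condition for counting a subject.

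**Two doses may mean two doses within the 6 weeks.** The text does not say so. On that reading, zero observation is excluded, but dose 2 on day 42 still leaves about one day.

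**The path is narrow.** The early toxicity must not itself be a DLT, and a related delay beyond 4 weeks ends talimogene laherparepvec. This stands: few subjects may be affected.

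**Much of the DLT risk may not depend on dose 2.** Pembrolizumab-related events count and pembrolizumab starts on day 1. The earlier SCCHN study in protocol 2.2, whose third cohort reached 10^8 PFU/mL, reports no grade 3 to 5 event related to talimogene laherparepvec. This also stands. The s = 100% column is an extreme, and the lower shares belong beside it.

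**Other reviews would see a late event.** The Dose Level Review Team reviews safety data as well as DLTs (10.4.3), all treated subjects enter the safety analysis, and 10.4.1.2 adds a review with 6 weeks of follow-up after more than 4 mL at 10^8 PFU/mL. This is fair mitigation, but none of it changes the DLT count.

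**The DLT decision is past.** SAP section 11 records that phase 1b was analysed and phase 3 dropped. This limits the fix. SAP section 1 still covers the follow-up and final analyses and the study report.

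**Conclusion.** The gap is in the text. The stated rules allow a subject to be scored as DLT-free with no observation after the first 10^8 PFU/mL dose, or about one day on the narrower reading. The error has one direction, because missed time can only lower the count. With 2 or 3 of 18 subjects affected, the chance of stopping at a true rate of 33% drops from 79% to 76.5% or 75% when a quarter of the risk follows dose 2, and to 69% or 63% when all of it does. The number affected and the risk share are assumptions. The calculation gives delayed subjects the same underlying risk as the others, so it does not model any extra risk they may carry.

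Two stronger readings are not supported. A reader might infer that the combination was wrongly found tolerable; the documents do not say how many subjects, if any, had a late dose 2. A reader might also infer that 81.6% is an arithmetic error; it can be reproduced, though only with a check after every subject and inferred limits. The point concerns what the DLT count observes, not how its power was computed.

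**What to change.** On the analysis side only: in protocol 3.1.1.1 and 10.1.2.1 and SAP 7.1, count a subject without a DLT as evaluable only if observed for a pre-stated minimum time after the first 10^8 PFU/mL dose. Otherwise treat the subject as not evaluable and replaceable under the existing rule.

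Because the primary analysis is done, keep the DLT Analysis Set as defined and apply this definition as a sensitivity analysis of DLT incidence in the remaining reports. List for each subject the days observed after dose 2 and any DLT-type event after the 6-week window.

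Lengthening the DLT window itself is not proposed. Sections 3.1.1.2, 6.2.1.2 and 6.2.2.2 tie discontinuation of study treatment to a DLT within that window, so moving it would change a treatment-stopping rule. The sponsor should reconcile the window with the delay and discontinuation rules; no dosing or stopping rule is suggested here.

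The cost is wording, one sensitivity table and one listing. The downside is that a few subjects may become non-evaluable, and in a prospective use would need replacement.

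### DLT evaluability: the definition and the replacement example disagree about a subject who takes both second doses and stops before week 6; the effect is small, but it touches the primary-endpoint denominator

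*Protocol*

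**What the plan says.** Protocol 3.1.1.1 sets the window: "The DLT evaluation period is 6 weeks from the initial administration of study treatment". For a subject without a DLT it sets two conditions. The subject "must have had the opportunity to be on treatment for at least 6 weeks from the initial dosing of study treatment", and must "have received at least 2 doses of talimogene laherparepvec and 2 doses of pembrolizumab in combination". Protocol 10.1.2.1 and SAP 7.1 carry the same two conditions into the DLT Analysis Set; the SAP again asks only that subjects "have had the opportunity to be on treatment for at least 6 weeks from the initial dosing of study treatment". None of these sections requires that treatment or observation actually reached week 6.

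Protocol 3.1.1.1 then allows replacement of subjects who are not evaluable. Its example is a subject who was never treated, or who "ended the study treatment before completion of DLT evaluation period for a reason other than experiencing a DLT". Sections 3.4 and 10.2.1 repeat the example. It sets no limit on the doses already received.

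The second talimogene laherparepvec dose is due "3 weeks (+ 3 days) after the initial injection" (Protocol 6.2.1.1), and pembrolizumab follows the same three-week cycle. About three weeks of the window therefore remain once the dose condition is met. SAP 3.1.1.1 refers the reader to Protocol 3.1.1.1 for the rules, where both texts stand. No section says which governs.

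**The concern.** DLT incidence is the phase 1b primary endpoint. Evaluability fixes its denominator, the Table 1 limit that applies at each look, and which subjects make up the first 18. A subject given two doses of each product who stops at week 4 or 5 for a reason other than a DLT is evaluable under the definition and non-evaluable under the example.

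The definition also has a gap of its own. A subject who dies of disease, or withdraws from observation, soon after the second doses still had the opportunity for six weeks. That subject enters as DLT-free although part of the window was never observed, and the bias runs towards declaring the combination safe.

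**Working it through.** **1. The plan's own figures.** Protocol 3.1.1.1 states a 7.7% one-sided level at a 10% DLT rate and 81.6% power at 33%. An exact binomial recursion gives 7.66% and 81.58% if the rule is checked after every subject with maxima of 1 DLT (n = 2–3), 2 (n = 4–8), 3 (n = 9–13) and 4 (n = 14–18). The limits at n = 2–3 and n = 14–17 are not printed in Table 1; they were found by search.

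The text plans three looks ("There will be up to 3 planned safety interim analyses"). With looks at 6, 12 and 18 and the printed maxima 2, 3 and 4, the probability of stopping is 4.6% at a 10% rate and 78.8% at 33%. By look, the 33% figure is 0.313 + 0.304 + 0.171 = 0.788. This is the baseline below. Its distance from 81.6% comes from how often one looks, not from evaluability.

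**2. Who remains observed after stopping treatment.** Protocol 3.1.4.1 and 9.2.2.1 collect adverse events through a safety visit 30 (+7) days after the last dose. With last doses at about day 22, that is day 22 + 30 = day 52, beyond day 42. Only death or lost observation cuts the window short.

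**3. How many die in the gap.** Assumption: the 8.4-month control-arm median OS from Protocol 10.2.2 applies to phase 1b, with constant hazard.
- Daily hazard = ln 2 / (8.4 × 30.44) = 0.002711.
- Survival to day 21 = exp(−0.002711 × 21) = 0.945; to day 42 = exp(−0.002711 × 42) = 0.892.
- Deaths between = 0.945 − 0.892, about 5.2%. In 18 subjects that is 18 × 0.052 = 0.9, or about one.

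**4. Effect on the stopping rule.** Assume 5% of subjects are counted with half their DLT risk observed.
- Effective rate = 0.33 × 0.95 + 0.33 × 0.05 × 0.5 = 0.3135 + 0.00825 = 0.32175.
- Stopping probability, looks 6/12/18 = 0.297 + 0.297 + 0.173 = 0.767, down from 0.788.

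**5. Direct reversal in Table 1.** The maximum is 2 for n = 4–8 and 3 for n = 9–13. Among these consecutive entries, one extra DLT-free subject changes the decision only at the step from 8 to 9 with 3 DLTs: 3/8 exceeds the limit of 2 and stops; 3/9 is within the limit of 3 and continues. Both sizes are allowed at Analysis #2 (4 + 4, or 4 + 5). With looks at 4 and 8, the probability of passing the first and then having exactly 3 DLTs in 8 is 25.2% at a 33% rate and 3.1% at 10%, before requiring an early stopper at that point. At 18, a reversal also needs the replacement subject to have a DLT (4/18 acceptable, 5/18 not).

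**The case against.** The best defence is that there is one definition, stated the same way in three places, and that the example sits inside a permissive clause that applies only once a subject is already non-evaluable. On that reading a subject with two doses of each product is evaluable, and replacement concerns enrolling a substitute rather than the denominator. SAP 8.1.1 and 10.5.1.1 do tie the DLT analyses to the DLT Analysis Set. The third doses fall at about the end of the window, so the example may simply have meant subjects who never reached the second doses. This is a reasonable reading, but no section states it, and the example appears three times without a dose limit. It also leaves the gap for death or lost observation untouched.

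Several stronger readings are tempting and are not supported:
- *Early stoppers contribute only days of observation at the higher concentration.* Step 2 shows that most remain under adverse-event follow-up for the whole window.
- *Some 10% to 16% of subjects are affected.* The upper figure treats every progression at the quoted 2.2-month median PFS as a stop that also ends observation. First scheduled imaging is at week 9 (Protocol 3.1.3.2), and clinically stable subjects may continue while progression is confirmed (Appendix D).
- *None of the affected subjects' risk is seen.* They have already been observed for the first three weeks.
- *Evaluability was chosen with the outcome in view.* The wording leaves room for judgement, but nothing in the documents shows that it was used this way.

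Deaths and intolerable toxicity that the investigator judges related are already DLTs (Protocol 3.1.1.2), which narrows the group further.

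**Conclusion.** The texts need to be reconciled, and the definition should not count a subject as DLT-free on an incomplete window. The size is modest: about 2 percentage points of stopping probability at a 33% DLT rate, and a direct reversal at a single step of Table 1. This rests on three assumptions: a phase 3 planning median applied to phase 1b, half the DLT risk observed in those who die, and looks at 6, 12 and 18. The documents report no DLT results, so they do not show that any decision was affected.

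SAP Section 11 records that the phase 1b primary analysis has been reviewed and that phase 3 will not proceed. The DLT looks are therefore complete and replacement is probably moot. What remains open is how the DLT Analysis Set is defined and reported in the clinical study report.

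**What to change.** State one rule, based on observation, in Protocol 3.1.1.1, 3.4, 10.1.2.1 and 10.2.1 and in SAP 7.1. A subject without a DLT is evaluable only if both products were given twice and DLT status was assessed through the end of the six-week period, whether or not treatment continued. In the replacement example, change *ended the study treatment* to *was not observed to the end of the DLT evaluation period*.

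Because the data have been reviewed, apply this through reporting rather than by silently redefining the set. List every subject with two doses of each product who stopped before week 6 without a DLT, with the date of the last DLT assessment. Report DLT incidence with and without those not observed to week 6, and record the change in SAP Section 11.

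The cost is wording, one listing, one additional row in the DLT table, and a slightly smaller denominator in the second figure.
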